2. LIST OF ABBREVIATIONS AND DEFINITIONS

AE	adverse event
ANCOVA	analysis of covariance
CNS	central nervous system
CRF	case report form
DMF	dimethyl fumarate
EDC	electronic data capture
EDSS	Expanded Disability Status Scale
eDiary	electronic diary
ET	early termination
GCP	Good Clinical Practice
Gd	gadolinium
GI	gastrointestinal
GSRS	Gastrointestinal Symptom Rating Scale
ICF	informed consent form
ICH	International Conference on Harmonisation
ITT	Intent-to-treat
IXRS	Interactive Voice and Web Response System
MMF	monomethyl fumarate
MRI	magnetic resonance imaging
MS	multiple sclerosis
Nrf2	nuclear factor (erythroid-derived 2)-related factor 2
PHI	protected health information
RNA	ribonucleic acid
RRMS	relapsing-remitting multiple sclerosis
SAE	serious adverse event
SUSAR	suspected unexpected serious adverse reaction
US	United States
USPI	United States Prescribing Information
Wk	week

Version 3

3. SYNOPSIS

This is a brief summary. For details, refer to the body of the protocol.

Protocol Number:	109MS414	
Protocol Title:	A Multicenter, Double-Blind, Placebo-Controlled Study of Montelukast on Gastrointestinal Tolerability in Patients With Relapsing Forms of Multiple Sclerosis Receiving TECFIDERA [®] (Dimethyl Fumarate) Delayed-Release Capsules	
Version Number:	3	
Name of Study Treatment:	TECFIDERA [®] (dimethyl fumarate)	
Study Indication:	Relapsing forms of multiple sclerosis (MS)	
Phase of Development:	4	
Rationale for the Study:	Two large Phase 3 studies (Study 109MS301 [DEFINE] and Study 109MS302 [CONFIRM]) and 1 Phase 2 study (Study C-1900) of dimethyl fumarate (DMF) in patients with relapsing-remitting MS demonstrated substantial benefits over placebo across a range of clinical and radiologic measures of disease activity. While the overall safety profile was favorable in these studies, the incidence of adverse events (AEs) associated with gastrointestinal (GI) tolerability, including diarrhea, nausea, abdominal pain, vomiting, and dyspepsia, was increased in DMF-treated patients compared with those who received placebo.	
	This study will investigate the impact of 10 mg montelukast once daily on GI tolerability in patients with relapsing forms of MS receiving DMF delayed-released capsules in order to potentially increase patient compliance and adherence to treatment and ultimately maximize the therapeutic potential of DMF.	
Study Objectives and	Objectives	
Endpoints:	Primary: The primary objective of this study is to evaluate whether montelukast can reduce the severity of GI events, measured by the Gastrointestinal Symptom Rating Scale (GSRS), after	
CONFIDENTIAL The information contained herein may not be used, disclosed, or published without the written consent of Biogen MA Inc. 11		

oral administration of DMF in subjects with relapsing forms of MS.

Secondary:

Secondary objectives in this study population are as follows:

- To evaluate whether montelukast after oral administration of DMF in subjects with relapsing forms of MS:
 - decreases discontinuations due to GI events
 - reduces the number of subjects taking symptomatic therapies for GI events
- To investigate the effect of montelukast on the incidence of flushing events after oral administration of 240 mg DMF in subjects with relapsing forms of MS

Exploratory:

Endpoints

Primary:

The primary endpoint of this study is the proportion of subjects with a worsening in the severity of GI AEs, measured by the average change from Day 0 to Day 10 in GSRS score. Day 0 is defined as the GSRS score of the day prior to the first dose of randomized study treatment.

[figure not shown]
Secondary:

The secondary endpoints of this study are as follows:

• Average change of GI severity scores from Day 0 to Day 10 as measured by total change of GSRS scores from Day 0 over the first 10 days (Day 1 to Day 10) divided by total number of days with GSRS recorded

CONFIDENTIAL

- Average change of GI severity scores from Day 0 to Week 10 as measured by total changes of GSRS score from Day 0 over the first 10 weeks (Day 1 to Week 10) divided by total number of days with GSRS recorded
- Time to first worsening of GSRS in GI severity
- Time to recovery to Day 0 GSRS score from the last occurrence of the worst score in GI severity
- Average change of GSRS score from Day 0 score to Weeks 1, 2, 3, 4, 5, 6, and 8
- Average change of GSRS score from Day 0 to 72 hours from the initiation of randomized study treatment
- Proportion of subjects who require GI symptomatic therapy during the study
- Percentage of subjects who discontinue DMF therapy due to GI-related AEs from Day 0 to Week 10
- Proportion of subjects who experience flushing events

Study Design:

This multicenter study will evaluate the effect of montelukast on GI tolerability in approximately 118 subjects with relapsing forms of MS treated with DMF. Subjects will enter a 2-week Screening Period and record pertinent information regarding GI-related events to allow characterization (using the GSRS score) of background GI-related events. Subjects will use an electronic diary (eDiary) to record GI events.

CONFIDENTIAL

Version 3

Subjects will be required to be \geq 75% compliant in the 14 days prior to randomization to remain eligible to participate in the study. Subjects will also use the eDiary to record DMF dosing, randomized study medication dosing, and any symptomatic concomitant medications/procedures. Subsequently, eligible subjects will initiate DMF therapy and record GI-related events in the eDiary for up to 28 days (DMF-GI Monitoring Period). During this period, subjects will take DMF, and GSRS scores will be monitored. Subjects who reach a specific threshold (GSRS score of >3in 1 question for 1 day or a GSRS score of ≥ 2 in 1 question for 2 consecutive days) will receive an alert through their eDiary to start taking randomized study treatment the same day, in accordance with the prescribing and labeling information. Subjects who do not meet the threshold by the end of the 28 days will be discontinued from the study. Eligible subjects, who reach the GSRS score threshold and initiate randomized study treatment (montelukast or placebo), will return to the study site at Weeks 0, 2, 4, 8, and at Week 10 for evaluation by study site staff (visits at Weeks 2 and 8 can alternatively be performed remotely by a contracted home health nurse). Weeks 2, 4, and 8 will have a visit window of ± 2 days, and Week 10 will have a visit window of \pm 3 days. The Safety Follow-Up Telephone Interview will be conducted 2 weeks (±5 days) after the Week 10 study visit or date of the Early Termination Visit.

Subjects who withdraw from the study after initiating randomized study treatment will not be replaced.

The dose of DMF used will be as described in the United States Prescribing Information (USPI). Subjects will take DMF for up to 14 weeks and the randomized study treatment (montelukast or placebo), concomitantly, for 8 weeks and record pertinent information regarding GI-related events in an eDiary.

Information on AEs and serious adverse events (SAEs) will be collected for possible correlation with GI-related events. For the purposes of this study, relapses of MS will not be considered AEs, and data related to relapses will only be captured if they are deemed an SAE or result in a subject's discontinuation. Relapses of MS resulting in hospitalization are considered SAEs but will not be reported as SAEs in the study unless the relapse is complicated by other SAEs or is

CONFIDENTIAL

fatal.

Rationale for Dose and Schedule Selection:	Dimethyl fumarate (DMF) will be taken in accordance with the USPI. The starting dose for DMF is 120 mg twice daily orally. After 7 days, the dose should be increased to the maintenance dose of 240 mg twice daily orally. Montelukast will be taken per product label: one 10-mg tablet once daily in the evening.
Study Location:	United States (US)
Number of Planned Subjects:	It is expected that approximately 295 subjects will be initially randomized to obtain the number of planned dosed subjects.
	Approximately 118 subjects in total will be dosed with randomized study treatment, with approximately 59 subjects dosed with randomized study treatment per treatment arm.
	Not all randomized subjects will be eligible to be dosed with randomized study treatment. Randomized subjects will be required to reach a predefined threshold of GI symptom severity before dosing with randomized study treatment will be initiated.
Study Population:	This study will be conducted in subjects with relapsing forms of MS. Detailed criteria are presented in the protocol.
Treatment Groups:	DMF + montelukast or DMF + placebo
Duration of Treatment and Follow-up:	The duration of a subject's participation will be up to 18 weeks, including a 2-week (+14 days) Screening Period, up to 14 weeks of DMF therapy, including 8 weeks of concomitant randomized study treatment, and the Safety Follow-Up Telephone Interview. Subjects who discontinue the study early will complete the same assessments specified for the Week 10 Visit.

Criteria for Evaluation:	forms candid	tudy is to be conducted in subjects with relapsing of MS. To be eligible to participate in this study, ates must meet the following eligibility criteria at the ing Visit:			
	1.	Have the ability to understand the purpose and risks of the study and provide signed and dated informed consent and authorization to use protected health information in accordance with national and local subject privacy regulations.			
	2.	Age ≥ 18 years at the time of informed consent.			
	3.	Reside in the US and have a confirmed diagnosis of a relapsing form of MS and satisfy the therapeutic indication as described in the local label.			
	4.	Female subjects of childbearing potential who are not surgically sterile must practice effective contraception during their participation in the study and be willing and able to continue contraception for 30 days after they complete or withdraw from the study. All men must practice effective contraception and should not donate sperm, throughout the study and for at least 90 days after their last dose of study treatment.			
	5.	As perceived by the Investigator, have the ability to comply with all requirements of the study protocol and to operate the eDiary required to record GI-related events.			
	Candidates will be excluded from study entry if any of the following exclusion criteria exist at the Screening Visit or at the timepoint defined in the individual criterion:				
	1.	Inability to comply with the study requirements or, at the discretion of the Investigator, is deemed unsuitable for study participation.			
	6.	Female subjects who are currently pregnant or breastfeeding or who are considering becoming pregnant during the study.			
	7.	History of significant GI disease (e.g., irritable bowel disease, peptic ulcer disease, history of major GI surgery, eosinophilic GI disease, or food allergies).			

8. Chronic use (\geq 7 consecutive days) of bismuth

CONFIDENTIAL

subsalicylate, simethicone, calcium carbonate, loperamide, proton-pump inhibitors, or ondansetron within 1 month prior to the Screening Visit. From Screening up to Day 10, use of such therapies is not permitted. From Day 11 (inclusive), subjects are permitted to take these therapies.

- 9. Use of the following medications: montelukast, immunotherapy, mast cell stabilizers, or parenteral, inhaled, or oral steroids up to 1 month prior to the Screening Visit. Use of these medications is also not permitted for the duration of the study (except for the use of montelukast as per study protocol) and will lead to discontinuation.
- 10. Treatment with montelukast is contraindicated for any reason.
- 11. Exposure to fumarates in the 3 months prior to the Screening Visit. Exposure is also not permitted for the duration of the Screening Period.
- 12. Have 1 or more major comorbidities that, in the opinion of the Investigator, may affect the outcome of the study.
- 13. History of malignancy (except for basal cell carcinoma that had been completely excised prior to study entry), severe allergic or anaphylactic reactions or known drug hypersensitivity, abnormal laboratory results indicative of any significant disease, and/or a major disease that would preclude participation in a clinical study.
- 14. Prior confirmed diagnosis or medical history of chronic eosinophilia.
- 15. Current enrollment in any other interventional clinical studies.
- 16. Subjects meeting the inclusion criteria as defined in Section 8.1, and who do not meet any of the exclusion criteria will be eligible to commence with a 2-week (+14 days) Screening Period. At the end of the Screening Period (at the Randomization Visit), GSRS scores and concomitant medication will be evaluated. Subjects who meet the following criterion will be discontinued and counted as screen failures: a GSRS score of ≥5 in 1 question for 1 day, a GSRS CONFIDENTIAL

score of \geq 4 in 1 question for 2 consecutive days, or a GSRS score of \geq 3 in 1 question for 3 consecutive days.

17. Subjects who did not meet the required eDiary compliance (≥75%) in the 14 days prior to randomization.

Efficacy:

An evaluation of whether montelukast administered with DMF reduces the severity of GI events as measured by GSRS scores will be performed. The use of symptomatic GI therapy will be monitored. The occurrence and frequency of discontinuations from DMF therapy due to GI-related events will be reported. In addition, the occurrence of flushing will be monitored.

Safety assessments include observation and evaluation of AEs and SAEs collected throughout the study. Demographics, baseline disease characteristics, vital signs, and clinical laboratory parameters will also be measured.

General Methods of Analysis

In general, continuous variables will be presented with summary statistics (mean, standard deviation, median, and range), and categorical variables will be presented with frequency distributions. All analyses will be conducted using 2-sided tests at the type I error rate (α -level) of 0.05 unless otherwise stated.

Primary Endpoint Analysis

Change from Day 0 to Day 10 in GSRS rating will be computed. The proportion of subjects with worsening, defined as increase in GSRS rating in GI AEs, will be estimated to obtain the rate of worsening in the 2 arms. The difference in the rate of worsening in GI AEs will be analyzed using a chi-square test and the logistic regression model adjusting for covariates and confounding factors.

Secondary Endpoints Analysis

The average change of GI severity score from Day 0 to Week 10 will be analyzed using an analysis of covariance (ANCOVA) model to adjust for covariates and confounding factors such as early drop-outs. Time to first worsening and time to recovery from the last worst GSRS score to Day 0 GSRS score will be analyzed using Kaplan-Meier methods and a Cox proportional hazards model. The average change

CONFIDENTIAL

The information contained herein may not be used, disclosed, or published without the written consent of Biogen MA Inc.

Safety:

Statistical Methods:

of GSRS score from Day 0 score at various timepoints will be analyzed using an ANCOVA model adjusting for covariates and confounding factors.

The proportion of subjects who require GI symptomatic therapy during the study period will be compared using the chi-square test. The percentage of subjects who discontinue DMF therapy due to GI-related events from the Randomization Visit to Week 10 will be summarized by treatment arm. The proportion of subjects who experience flushing events in each treatment group will also be summarized.

Exploratory Endpoints Analysis

No interim analysis will be performed.

Interim Analysis:

Sample Size Determination: Assuming t

[figure not shown]
Assuming that 40% of the placebo subjects will be improving (by chance) without any intervention, a total sample size of 118 (dosed with randomized study treatment), 59 per treatment arm (after randomization), would provide approximately 80% power to detect a 30% difference between the treatment arm and placebo arm in proportion of subjects with any improvement in GI severity, as measured by the average change from Day 0 in GSRS score to Day 10, including an early discontinuation of 15%.

Version 3

4. STUDY SCHEMATIC AND SCHEDULE OF EVENTS FOR STUDY 109MS414

4.1. Study Schematic

Figure 1: Study Design

Abbreviations: BID = twice daily; DMF = dimethyl fumarate; GI = gastrointestinal; QD = once daily. *Use of symptomatic therapies, as specified in Section 10.3.2, is permitted from Day 10 onward.

4.2. Schedule of Events

Table 1:Schedule of Events

Assessment	Screening Visit ^a	Screening Period (2 Weeks +14 Days)	Randomization Visit ^a (Week -4)	DMF-GI Monitoring Period (up to 28 Days)	Wk 0 ^{a,b}	Wk 2 ^c	Wk 4 ^a	Wk 8 ^c	Wk 10 ^a /ET	Safety Follow- Up ^d (± 5 days)
Clinic Visit	Х		х		Х	х	х	Х	Х	
Informed Consent	Х									
Eligibility Criteria	Х		X ^e							
Demographics	Х									
Vital signs ^f	Х									
Medical History (incl. MS disease status) ^g	Х									
Alcohol Consumption	Х									
Tobacco Use	Х									
Pregnancy Testing ^h	Х		х							
Concomitant Medications/ Procedures	Х		х		х	х	х	х	х	Х
Blood Biomarkers (optional) ^j			х				Х		Х	
Dispense eDiary	Х									
eDiary Training	Х									
eDiary Entries (Daily) ^k										
Return eDiary to Clinical ^l			X ^m	X ^m					х	

Version 3

Protocol 109MS414 Phase 4 Study of GI Tolerability in DMF-Treated Subjects With Relapsing Forms of MS

Assessment	Screening Visit ^a	Screening Period (2 Weeks +14 Days)	Randomization Visit ^a (Week -4)	DMF-GI Monitoring Period (up to 28 Days)	Wk 0 ^{a,b}	Wk 2 ^c	Wk 4 ^a	Wk 8 ^c	Wk 10ª/ET	Safety Follow- Up ^d (± 5 days)
Dispense DMF With Dosing Instructions			Х							
DMF Administration (Daily)			DMF administration will occur every day as per the USPI							
Randomization			Х							
Dispense Randomized Study Treatments			X ⁿ							
Randomized Study Treatment Administration (Daily)					Randomized study treatment administration will occur every day as per the prescribing information.					
SAEs	SAE data will be collected from the signing of the informed consent up to the Safety Follow-Up Telephone Interview. MS relapses resulting in hospitalization are considered SAEs but will not be reported as SAEs in the study unless the relapse is complicated by other SAEs or is fatal.									
AEs				AE data will be collected from the first dose of DMF up to the Safety Follow-Up Telephone Interview.						

Note: Weeks 2, 4, and 8 will have a visit window of ± 2 days, and Week 10 will have a visit window of ± 3 days.

Abbreviations: AE = adverse event; DMF = dimethyl fumarate; DNA = deoxyribonucleic acid; eDiary = electronic diary; EDSS = Expanded Disability Status Scale; ET = early termination; GI = gastrointestinal; GSRS = Gastrointestinal Symptom Rating Scale; (Compared to the state of th

; MS = multiple sclerosis; ; RNA = ribonucleic acid; SAE = serious adverse event; USPI = United States Prescribing

Information;Wk = week.

^a This visit must be performed in clinic.

^b Subjects will receive an alert through the eDiary if their GSRS scores reach the appropriate threshold. This alert will tell the subject to begin taking the randomized study treatment the same day. At this time, study site should arrange the Week 0 Visit as soon as possible after the first administration of randomized study treatment. Visit dates will be measured from the first administration of randomized study treatment.

^c This visit may be performed remotely if more convenient for the subject; site must telephone the subject to document concomitant medications/procedures and AEs.

^d The safety follow-up will be performed as a telephone interview 2 weeks (±5 days) after the Week 10/ET visit.

^e GI symptom and eDiary compliance assessment.

^f Including height and weight measurements and vital signs (temperature, blood pressure, and sitting blood pressure).

^g Medical history, including MS disease status, will include collection of information on duration of MS, relapse history, EDSS score, and treatment for MS.

^h Dipstick test (only for women of childbearing potential).

CONFIDENTIAL

^j Serum, RNA, and DNA samples will be collected for biomarker analysis and future use analysis in subjects who provide additional consent. A single DNA sample can be taken at any of prespecified timepoints.

Version 3

^k Subjects will be required to record their daily GI symptoms in the eDiary every day from the Screening Visit up to Week 10.

¹ eDiaries will be returned if (1) the subject fails during the Screening Period, (2) the subject does not reach the required GI symptom threshold during the DMF-GI Monitoring Period, or (3) the subject completes or discontinues the study.

^m Subjects who do not reach the GI symptom threshold during the DMF-GI Monitoring Period (a GSRS score of ≥ 5 in 1 question for 1 day, ≥ 4 in 1 question for 2 consecutive days, or ≥ 3 in 1 question for 3 consecutive days) will be discontinued.

ⁿ Subjects are dispensed randomized study treatment at this visit but must not begin taking the medication until alerted about their eDiary.

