4.3. Additional Information

After initial eligibility has been confirmed at the Screening Visit, subjects will enter a 2-week (+14 days) Screening Period. At the end of this period, eligible subjects will return to the clinic for a Randomization Visit. The eligibility criteria will be rechecked, and additionally, the gastrointestinal (GI) symptoms noted in an electronic diary (eDiary) will be assessed. Individuals with Gastrointestinal Symptom Rating Scale (GSRS, Section 4.4) score of ≥ 5 in 1 question for 1 day, a GSRS score of >4 in 1 question for 2 consecutive days, or a GSRS score of \geq 3 in 1 question for 3 consecutive days will be discontinued and counted as screen failures. An eDiary compliance check will also be performed. Subjects will be required to be >75%compliant in the 14 days prior to randomization to remain eligible to participate in the study. Subjects who fulfill the eligibility criteria and meet the GI symptom assessment criteria will be randomized to 1 of 2 treatment arms. At this time, subjects will start commercial dimethyl fumarate (DMF) and will receive (but will not begin taking) their randomized study treatment. Subjects will then enter the DMF-GI Monitoring Period (up to 28 days). During this period, subjects will take DMF and note their daily GI symptoms in the eDiary. If at any time during this period, the GSRS scores noted are >3 in 1 question for 1 day or >2 in 1 question for 2 consecutive days, the subject will receive an alert through his/her eDiary to start taking the randomized study treatment the same day. Any subjects who do not reach this threshold during the 28-day period will be discontinued from the study. It will be the decision of the Investigator to continue with DMF therapy after the subject has been withdrawn from the study.

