7.2.4. DMF-GI Monitoring Period

The duration of the DMF-GI Monitoring Period will be up to 28 days. On the first full day after the Randomization Visit, subjects will start taking DMF per the prescribing instruction. Subjects

CONFIDENTIAL

will make daily entries in the eDiary, recording pertinent information regarding GI-related events to allow the characterization of events that occur while taking DMF. During this period, if a subject meets the threshold of a GSRS score of ≥ 3 in 1 question for 1 day or a GSRS score of ≥ 2 in 1 question for 2 consecutive days, the subject will receive an alert through his/her eDiary to begin taking the randomized study treatment the same day. Any subject who does not reach the GSRS threshold during the DMF-GI Monitoring Period will be discontinued.

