9.2. Randomization of Subjects

Subjects must be consented before any screening baseline tests or assessments are performed. At the time of consent, the subject will be registered into the study. Participating study sites are required to document all registered candidates initially considered for randomization in the study. If the subject is not randomized in the study, the reasons will be documented in the subject's source documents and on the registration log.

Subjects will be randomized at the Randomization Visit. At this visit, eligible subjects will be randomized to 1 of 2 treatment arms (DMF + montelukast or DMF + placebo) in a 1:1 ratio. Subjects will be instructed not to take the blinded randomized study treatment until they receive an alert through their eDiary. This alert will appear if a subject meets the criteria of GSRS score of ≥ 3 in 1 question for 1 day or a GSRS score of ≥ 2 in 1 question for 2 consecutive days.

No subjects may begin treatment prior to randomization and assignment of a unique subject identification number. Any subject identification numbers that are assigned will not be reused, even if the subject does not receive treatment. Subject identification numbers will be assigned by the Interactive Voice and Web Response System (IXRS).

Refer to the Study Reference Manual for details on registration.

As confirmation, Biogen will provide the Investigator with verification of the subject's registration.

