3.1 Definition of the GSRS threshold

Two definitions of the GSRS threshold were used in this study.

Definition in the version 1 of the protocol: GSRS score of ≥ 5 in one question for 1 day or a GSRS score of ≥ 4 in one question for 2 consecutive days or GSRS score of ≥ 3 in one question for 3 consecutive days.

Definition in the 2^{nd} and higher Protocol versions: GSRS score of ≥ 3 in one question for 1 day or a GSRS score of ≥ 2 in one question for 2 consecutive days.

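### Footnote m to the Schedule of Events, in protocol version 3 and in the SAP, still discontinues Monitoring Period subjects by the superseded version 1 GSRS threshold

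*Combined protocol and SAP*

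**What the plan says.** Under Table 1 in Protocol 4.2, footnote m reads "Subjects who do not reach the GI symptom threshold during the DMF-GI Monitoring Period (a GSRS score of ≥ 5 in 1 question" for one day; it then adds at least 4 on two consecutive days and at least 3 on three consecutive days, and says that subjects who do not get there are discontinued. Footnote m under SAP Table 1 is word for word the same.

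Protocol 7.2.4, which governs this period, gives a different rule: "the threshold of a GSRS score of ≥ 3 in 1 question for 1 day or a GSRS score of ≥ 2" on two consecutive days. It attaches the consequence directly: "Any subject who does not reach the GSRS threshold during the DMF-GI Monitoring Period will be discontinued". Protocol 9.2 uses the same criterion for the eDiary alert that starts randomized treatment: "This alert will appear if a subject meets the criteria of GSRS score of ≥ 3 in 1 question for 1 day", or at least 2 on two consecutive days.

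The SAP section titled Definition of the GSRS threshold explains where the two rules come from. For the older one it says "Definition in the version 1 of the protocol: GSRS score of ≥ 5 in one question for 1 day", followed by the 4-for-two-days and 3-for-three-days branches. For the second "and higher Protocol versions: GSRS score of ≥ 3 in one question for 1 day or a GSRS score of ≥ 2" on two consecutive days. SAP section 1 states that the SAP is based on protocol version 3.

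**The concern.** Both footnotes are operative text in current documents, not entries in a list of changes. Each document therefore contradicts itself on the threshold that decides whether a subject in the DMF-GI Monitoring Period goes on to randomized treatment or leaves the study.

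Site staff are likely to use the Schedule of Events as a quick reference. Footnote b there speaks only of the appropriate threshold and footnote l only of the required one, and Section 12 makes failure of the GSRS criteria a mandatory withdrawal without restating the numbers. Footnote m is the only note to the table that gives figures for this decision, and they are the wrong ones. A site that took it at face value would discontinue, and collect the eDiary from, subjects whose milder symptoms qualify under the current rule.

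**Working it through.** No sample size, power or alpha figure is involved. The check has two parts: which rule is current, and whether the two rules can lead to different decisions.

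**1. The places side by side.** 5/4/3 means ≥5 for one day, ≥4 for two consecutive days or ≥3 for three consecutive days, on one question. 3/2 means ≥3 for one day or ≥2 for two consecutive days, on one question.

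| Place | Rule | Effect |
|---|---|---|
| Protocol Table 1, footnote m | 5/4/3 | not reached in Monitoring Period: discontinue |
| SAP Table 1, footnote m | 5/4/3 | same |
| SAP, Definition of the GSRS threshold | 5/4/3 for version 1; 3/2 for version 2 and higher | defines the threshold |
| Protocol 7.2.4 | 3/2 | reached: alert; not reached: discontinue |
| Protocol 9.2 | 3/2 | reached: alert |
| Protocol 4.3 and synopsis | 3/2 | reached: alert; not reached: discontinue |
| Protocol 7.2.2 and 7.2.3 | 5/4/3 | reached in Screening Period: screen failure |

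Some signs in 4.3 and the synopsis appear as > in the text available to me. I read them as ≥ lost in conversion, since 7.2.4, 9.2 and the SAP print ≥. Nothing here depends on it.

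**2. Is footnote m just the screening rule?** The numbers match, and marker m also appears in the Randomization Visit column. But screening removes subjects who do reach 5/4/3, before randomization. Footnote m removes subjects who do not reach it, and names the Monitoring Period. The two run in opposite directions.

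**3. Direction of the conflict.** Every branch of 5/4/3 contains at least one day at ≥3, and one such day alone satisfies 3/2. So whoever meets footnote m also meets the current rule. The converse fails: one isolated day at 3 or 4, or two consecutive days at 2, satisfies 3/2 but not 5/4/3.

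**4. Enumeration as a check.** Take one question scored 0 to 6 (Protocol 4.4) and list all 7^n score patterns over n days. For n = 2:

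- 3/2 is missed when both scores are 0 to 2, except the pair (2,2): 9 − 1 = 8, so 49 − 8 = 41 meet it.
- 5/4/3 is missed when both scores are 0 to 4, except the pair (4,4): 25 − 1 = 24, so 49 − 24 = 25 meet it.
- Meeting 3/2 only: 41 − 25 = 16.

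| Days | Patterns | Meet 3/2 | Meet 5/4/3 | 3/2 only | 5/4/3 only |
|---|---|---|---|---|---|
| 2 | 49 | 41 | 25 | 16 | 0 |
| 3 | 343 | 321 | 232 | 89 | 0 |
| 4 | 2,401 | 2,341 | 1,879 | 462 | 0 |

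Any day at ≥5 meets both rules and a peak of 1 or less meets neither, so every pattern in conflict peaks at 2, 3 or 4. The counts weight all patterns equally on one of 15 questions over a few days of a period of up to 28. They confirm the direction and are not probabilities.

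**The case against.** The best defence is that the footnote has little to act on. Footnotes b and n in the same table make the eDiary alert the trigger for dosing, and under 9.2 the alert fires at 3/2. A subject with one day at 3 has then already been told to start treatment, and the site is directed to arrange the Week 0 Visit. To do harm, a site would have to recheck diary scores by hand against footnote m and override the alert; no step asks for that. Marker m sits only on the eDiary-return row. The correct consequence stands in 7.2.4, in 4.3 ("Any subjects who do not reach this threshold during the 28-day period will be discontinued from the study") and in the synopsis ("Subjects who do not meet the threshold by the end of the 28 days will be discontinued from the study"), each next to the 3/2 threshold. All of this stands, and it is why the practical risk is low. It does not make the printed figures right.

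The SAP half is weaker still. The SAP says that both definitions were used in the study, so 5/4/3 is a true part of its history, and a SAP footnote does not direct site conduct. That also stands, but the SAP footnote presents 5/4/3 as the threshold without saying that it belongs to version 1.

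A reader might go further and infer that the wrong subjects were dosed or dropped, or that the analysis set is compromised. The documents do not support this. They report no subject handled under the footnote. The modified ITT population in SAP 7.1.1 is defined by dosing and by at least one GSRS score from Day 1 to Day 10, not by the threshold. Nor is Section 12 left without a referent, since 7.2.4 supplies one.

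**Conclusion.** The inconsistency is real and both footnotes are wrong as they stand for version 2 and higher. If the footnote were followed, the error would run one way: qualifying subjects whose scores peak at 2 to 4 would be wrongly discontinued, and nobody would be wrongly kept. The likelihood is low, and no analysis, population definition, alert or screening rule is affected. It deserves correction because it is a wrong decision threshold in the Schedule of Events, not because it threatens the result.

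The conclusion rests on the SAP's own attribution of each rule to a protocol version, and on the alert being programmed as 9.2 describes. The share of subjects who could be affected cannot be derived from the documents, and the pattern counts should not be read as an estimate of it. A reader might also infer that the threshold applying to a subject follows from the protocol version at that subject's enrollment. The SAP ties each definition to a protocol version only. It does not say what applied to someone still in monitoring when version 2 took effect.

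**What to change.** Protocol, footnote m: replace the parenthesis with the current threshold, namely a score of ≥3 on 1 question for 1 day, or ≥2 on 1 question on 2 consecutive days.

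SAP, footnote m: make the same replacement and add a pointer saying that the protocol version 1 definition is given under Definition of the GSRS threshold. Cite that section by title, because the SAP numbers two sections 3.1. Do not add wording that assigns a definition by version at enrollment.

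Cost: in the SAP, one footnote and no change to any analysis. In the protocol, one parenthesis; but amendments go to the IRBs (Section 19.3), about 50 sites are planned (7.1), and SAP section 5 closes enrollment at approximately 60 subjects randomized and dosed up to Day 10. A stand-alone amendment is not warranted. A written clarification to sites while subjects are still in the Monitoring Period, or a correction in the next amendment if there is one, is enough.
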